## Statistical Analysis Plan

---

### 4.5 Other outcome measures

- Proportion of days with thrombocytopenia (platelet count  $<10 \times 10^9/L$ ) from consent up to study day 30 will be compared by treatment arm using binary logistic regression analysis (thrombocytopenic or not on any given day). Correlation at participant level will be accounted for by including a random participant effect. If the number of thrombotic events is very small, the proportions will simply be described by arm.
- Proportion of days with thrombocytopenia (platelet count  $<30 \times 10^9/L$ ) from consent up to study day 30 will be compared by treatment arm using binary logistic regression analysis (thrombocytopenic or not on any given day). Correlation at participant level will be accounted for by including a random participant effect. If the number of thrombotic events is very small, the proportions will simply be described by arm.
- Proportion of days with thrombocytopenia (platelet count  $<50 \times 10^9/L$ ) from consent up to study day 30 will be compared by treatment arm using binary logistic regression analysis (thrombocytopenic or not on any given day). Correlation at participant level will be accounted for by including a random participant effect. If the number of thrombotic events is very small, the proportions will simply be described by arm.
- Proportion of days with fever (highest daily temperature  $\geq 38.1^\circ\text{C}$ ) of days spent in hospital, up to study day 30, will be analysed using binary logistic regression analysis (fever or not on any given day). Correlation at participant level will be accounted for by including a random participant effect.
- Reasons for platelet and red cell transfusions will be described by arm.
- A plot depicting median, IQR platelet count over time from consent up to study day 30, by arm, will be produced. Where consent, randomisation and/or treatment occurred on the same day, the participant's platelet count will only be included in the median calculation for the last of the concurrent events.
- A plot depicting overall survival from randomisation up to study day 120, by arm, will be produced.
- Trial treatment will be summarised by arm, including number of participants who changed route or frequency, number of participants who missed a dose, reasons for discontinuation of treatment. Median, IQR number of days on trial treatment and on oral trial treatment, from the first day of treatment administration until discontinuation of trial treatment, for participants who received at least one dose of trial treatment, will be estimated using competing risks analysis. Death prior to discontinuation of trial treatment will be considered as the competing risk.
- Number of granulocyte transfusions/participant up to study day 30 will be summarised by treatment arm..
- Location of bleeding up to study day 30 will be summarised, by treatment arm
- Number of participants requiring interventions and procedures for bleeding up to study day 30 will be summarised by treatment arm. This may be sub-categorised by type of intervention or procedure if there are large numbers of participants requiring interventions and procedures.
- Number of participants requiring concomitant medication (categorised as medication increasing risk of bleeding, medication decreasing risk of bleeding, no concomitant medication) up to study day 30 will be summarised by treatment arm. This may be sub-categorised by type of concomitant medication if there are large numbers of participants requiring concomitant medication.
- Number of participants on Mylotarg during the first 30 days of the trial will be summarised by treatment arm.

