1.7. Specific objectives or hypotheses

The hypothesis is that in patients with haematological malignancies, during a period of severe thrombocytopenia, prophylactic use of antifibrinolytics would decrease bleeding and the demand for platelet transfusions. There may also be additional benefits for patients such as improved quality of life during their in-patient stay and earlier discharge home. Given the importance of understanding the cost-effectiveness of new treatments, this trial proposal will also incorporate a health economic analysis.

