6.2.6. Discontinuation of Trial treatment

The trial treatment will be permanently discontinued as soon as any one of the following situations occurs:

1. It has been 30 days since the participant first started the randomised trial treatment.
2. The participant has a spontaneous increase in platelet count from $<30 \times 10^9/L$ to $>50 \times 10^9/L$.
3. The participant has had 3 consecutive days with morning platelet counts $>30 \times 10^9/L$, and no requirement for platelet or granulocyte transfusion, or stem cell transplant.
4. The participant receives open label tranexamic acid, other antifibrinolytic agent or procoagulant drug, (e.g., DDAVP, recombinant Factor VIIa, or Prothrombin Complex Concentrates). Use of these agents will be recorded in trial data.
5. The participant begins anticoagulant or antiplatelet therapy.
6. The participant has visible haematuria.
7. The participant has a diagnosis of thrombosis.
8. The participant becomes anuric (defined as urine output $<10 \text{mls/hr}$ over 24 hours).
9. The participant develops sinusoidal obstructive syndrome (SOS, Veno-occlusive Disease, VOD)

Note: If the trial treatment is discontinued it must not be restarted while the participant remains in the trial.

In addition to the reasons stated above participants may stop treatment early or be stopped early for any of the following reasons:

- Disease progression.
- Unacceptable adverse reaction
- Any change in the participant's condition that justifies the discontinuation of treatment in the opinion of the clinician.
- Withdrawal of consent.

In consenting to the trial, participants are consenting to the trial treatment, trial follow up and data collection. As the participant's participation in the trial is entirely voluntary they may choose to discontinue the trial treatment at any time without penalty or loss of benefits to which they are otherwise entitled. Although the participant is not required to give a reason for discontinuing their trial treatment, a reasonable effort should be made to establish this reason whilst fully respecting the participant's rights.

Participants will remain in the trial for the purpose of follow up and data analysis, unless they withdraw their consent from all stages of the trial, in which case, they should be withdrawn. Data collected up until the time of withdrawal will be retained and included in the analysis.

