8.4. Other Measurements

The following data will be collected:

Demographics and Medical History

This will include:

- Weight

- Height
- Date of birth
- Gender
- Ethnic origin
- Diagnosis (disease and type or treatment: i.e. chemotherapy or type of stem cell transplant)
- If receiving allogeneic transplant, whether HLA matched or mismatched
- Type and date of transplant or first day of other treatment
- Previous co-morbidities
- Renal impairment
- Previous fungal infection

Laboratory Studies (All study centres)

- Urine dipstick (at enrolment)
- Haemoglobin and platelet count, required daily when participant is an in-patient and 3 times a week, or as Standard of Care, when participant is an out-patient
- Coagulation profile (PT or INR), at randomisation.
- Serum creatinine (required at enrolment, randomisation, study days 1&2, and then 3 times a week on Monday, Wednesday and Friday, or as SOC, when participant is on trial treatment)
- Liver function tests including bilirubin and albumin required if VOD suspected / reported three times a week
- HLA antibody screen - required at enrolment, and repeated if a participant develops platelet refractoriness (defined as two sequential transfusions with a 24 hour platelet increment $<5 \times 10^9/L$)

Laboratory Studies (Selected study centres)

- Fibrinolysis assay (central/local lab) – sub-study
- C-reactive protein (CRP) (this is required daily when participant is an in-patient if it is measured routinely at the participating hospital)
- Immature platelet fraction (this is required daily when participant is an in-patient and at least 3 times per week, when participant is an out-patient)

Transfusions given during study (from enrolment to study day 30)

- Data on platelet, granulocyte or stem cell transfusion
 - Reason for transfusion (prophylaxis, invasive procedure, active bleeding, risk of significant bleeding, other)
- Data on red cell transfusions
 - Number of units transfused
 - Reason for transfusion (anaemia, active bleeding, other)

Fever

- Highest temperature within each 24 hour period (defined as 8am to 8am) when participant is an inpatient

Quality of Life Assessment

- Quality of life assessment (EQ5D & FACT-Th) at randomisation, day 12 (± 2) and day 30 (± 2). EQ-5D at day 120 (± 7).

Health economic analysis (from study day 1 to study day 120)

- Number of hospital admissions, and duration of stay
- Number of ITU admissions and duration of stay
- Number of day unit admissions

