### 4.2 Analysis principles

Unless otherwise specified, all tests will be two-sided and p-values of less than 0.05 will be considered as evidence of a difference between treatment arms.

Multiple comparisons will be performed and this may increase the probability of observing a statistically significant result by chance. No adjustments will be made to account for multiple testing.

P-values will be reported to four decimal places with p-values less than 0.00005 as <0.0001. SAS or R will be used to conduct analyses.

All analyses will be adjusted for the stratification variable (recruitment site). Recruitment site will be accounted for by including a random effect in each model.

All hazard, odds and rate ratios will be presented as active treatment versus placebo. A ratio which is greater than 1 indicates that the hazard, odds or rate is greater in the active treatment arm. 95% confidence intervals will be presented with all ratios. P-values for regression models will be obtained by comparing  $-2 \times \log\text{-likelihood}$  values for models with and without the treatment term.

The key demographics and clinical condition of the participants at consent will be presented for each arm of the trial to describe the cohort. A CONSORT diagram will be presented to show how participants progressed through the trial.

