### 4.8 Procedures for handling Missing Data

For all outcomes, the volume of missing data will be summarised by treatment arm.

Participants withdrawn or lost to follow up before day 30 will be included in the primary outcome analysis (and in secondary outcome analyses where possible), censoring at the time that they withdrew/were lost to follow up.

It is expected that deaths and other safety outcomes, other than for participants withdrawn or lost to follow up, will be fully reported.

For the main analysis of the primary outcome, any missing bleeding assessments during the 30-day follow up period or to the last point of contact, whichever is first, will be assumed to be grade 1 or below. Sensitivity of the primary outcome to missing data will be assessed as per the sensitivity analysis described above.

Missing values for secondary and baseline characteristics will not be imputed. Missing data will be excluded from the relevant analyses.

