### 5.7 Other Outcome summary tables

**Table xx Proportion of days with thrombocytopenia**

Outcome	Active arm (n=)	Placebo arm (n=)	Overall (n=)	P value
Proportion of days with thrombocytopenia (<math><10 \times 10^9/L</math>) from randomisation up to study day 30 - % (95% CI)				
Odds ratio (95% CI)				
Proportion of days with thrombocytopenia (<math><30 \times 10^9/L</math>) from randomisation up to study day 30 - % (95% CI)				
Odds ratio (95% CI)				
Proportion of days with thrombocytopenia (<math><50 \times 10^9/L</math>) from randomisation up to study day 30 - % (95% CI)				
Odds ratio (95% CI)				
Proportion of missing platelet counts from randomisation up to study day 30 – n/N (%)				
All analyses are adjusted for centre and participant.				

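### Days at home are under-weighted in the thrombocytopenic-days analysis: the reported proportion is distorted in both arms and, if discharge timing differs by arm, so is the comparison

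*SAP*

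**What the plan says.** Three rules combine.

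- **Measurement.** Protocol 8.4 states that haemoglobin and platelet counts are "required daily when participant is an in-patient and 3 times a week, or as Standard of Care, when participant is an out-patient". The schedule tables mark a count in every day column; Protocol 8.4 gives the out-patient exception.
- **Model.** For each of three thresholds (10, 30 and 50 × 10⁹/L), SAP 4.5 says that the proportion of days "will be compared by treatment arm using binary logistic regression analysis (thrombocytopenic or not on any given day"). The model has a random participant effect and, under SAP 4.2, a random site effect. It has no term for study day or for place of care.
- **Missing data.** SAP 4.8 states: "Missing values for secondary and baseline characteristics will not be imputed. Missing data will be excluded from the relevant analyses". The other outcomes are section 2.2.3 of the SAP, under the secondary outcome heading.

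The results table in SAP 5.7 includes a row for "Proportion of missing platelet counts from randomisation up to study day 30" by arm, but nothing adjusts for it. The imputation in SAP 4.7 covers bleeding assessments only. For fever, SAP 4.5 does set a denominator: the proportion "of days spent in hospital, up to study day 30, will be analysed using binary logistic regression analysis". For platelets it sets none.

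**The concern.** Whether a day has a count depends on whether the participant is in hospital, and discharge is related to recovery. The analysed days are therefore not a fair sample of the 30. A random intercept per participant does not correct unequal sampling of days within a participant.

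The reported level is wrong in both arms even if the arms are handled alike. The comparison also depends on when each arm goes home. Protocol 1.7 lists, as possible additional benefits of treatment, "improved quality of life during their in-patient stay and earlier discharge home". If discharge timing does differ, identical platelet courses can produce different proportions. SAP 4.2 says that "p-values of less than 0.05 will be considered as evidence of a difference between treatment arms", without adjustment for multiple testing. Such a result could be misread as an effect of tranexamic acid on platelet recovery, or as unequal time at bleeding risk.

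**Working it through.** The documents give no figure for this outcome, so there is none to reproduce. They also give no length of stay or duration of low counts. The values below are assumptions, apart from the 3-in-7 rate (Protocol 8.4) and the 30-day window.

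**Level.** Let counts be at or below 30 on days 1 to 15 and above it afterwards, d the last day in hospital, and f = 3/7 the share of home days with a count. The true proportion is 15/30 = 50.0%.

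- Analysed days: N = d + (30 − d) × f
- Analysed low days: L = 15 if d ≥ 15, otherwise L = d + (15 − d) × f
- Reported proportion = L/N; odds = L/(N − L)

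| d | L | N | Reported | Odds |
|---|---|---|---|---|
| 10 | 12.14 | 18.57 | 65.4% | 1.889 |
| 12 | 13.29 | 19.71 | 67.4% | 2.067 |
| 13 | 13.86 | 20.29 | 68.3% | 2.156 |
| 15 | 15 | 21.43 | 70.0% | 2.333 |
| 16 | 15 | 22.00 | 68.2% | 2.143 |
| 17 | 15 | 22.57 | 66.5% | 1.981 |
| 19 | 15 | 23.71 | 63.3% | 1.721 |
| 22 | 15 | 25.43 | 59.0% | 1.438 |

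The level is 59% to 70% against a true 50% at every discharge day shown. With weekly counts at home (f = 1/7) and d = 19, N = 20.57 and the level is 72.9%.

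**Comparison, identical platelet courses, earlier against later discharge.**

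- Day 17 v 19: 1.981/1.721 = 1.15
- Day 16 v 19: 2.143/1.721 = 1.24
- Day 13 v 16: 2.156/2.143 = 1.01
- Day 10 v 12: 1.889/2.067 = 0.91

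The sign depends on whether discharge falls after or before recovery.

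**The planned model, simulated.** Random-intercept logistic regression with a likelihood ratio test, 293 per arm (586/2), no site effect, and the same platelet recovery in both arms.

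- Last low day with mean 15 (SD 4, 6 or 8), discharge on average 4 days later, counts on 3 fixed weekdays at home. With equal discharge the odds ratio is 1.00 and p < 0.05 occurs in 4% to 8% of trials. With one arm discharged 2 days earlier, the odds ratio is 1.13 to 1.14 and p < 0.05 occurs in 85%, 41% and 25% (SD 4, 6, 8).
- Mean of 12 low days, discharge on average 8 days later, each home day counted with probability 3/7. With no gap the odds ratio is 1.00 (p < 0.05 in 3%). With a 2-day gap it is 1.10 (39%), or 1.23 (97%) if counts are weekly. If most participants go home while still low, a 2-day gap gives 0.93 (18%).
- Same set, every day classified, 4-day gap: odds ratio 1.005 (3%).

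**Remedies in the worked example.** With Monday/Wednesday/Friday counts, the number of unmeasured days before the next count, starting from each weekday Monday to Sunday, is 0, 1, 0, 1, 0, 2, 1: mean 5/7 = 0.714.

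- Carry-forward, d ≤ 15: (15 + 0.714)/30 = 52.4%. Weekly, the mean wait is 3 days: 18/30 = 60.0%. For day 13 v 16 this creates a false odds ratio of 15.714/14.286 = 1.10 (18/12 = 1.50 weekly), where the planned analysis gives 1.01.
- Nearest recorded count, ties split equally: 50.0% for discharge well before or any time after recovery. The worst case is d = 15, with (15 + 0.714/2)/30 = 51.2%, odds 1.05 against 1.00. Weekly, the worst case is (15 + 3/2)/30 = 55.0%.
- Hospital days only, as for fever: 15/19 = 78.9% v 15/16 = 93.8% for a 3-day gap, which is worse than the plan.

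**The case against.** The strongest objection is that no false difference arises without a discharge gap. Protocol 1.7 offers earlier discharge only as something that may happen, and site staff are blinded (Protocol 5.8). This stands: with equal discharge the comparison is fair and only the level is wrong.

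A reader might infer that the plan will show more thrombocytopenic days on tranexamic acid. The documents do not support that. Protocol 6.1 provides for discharge on oral treatment before the stopping criteria are met, and if that is common the sign reverses. The simulated rejection rates also depend heavily on invented spreads.

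Only the 30 threshold and a single clean recovery were worked through. Recovery past 50 comes later, so more low days fall at home. Counts near 10 move with transfusion. The weighting problem applies to all three thresholds, but its size and sign may differ.

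Two readings are inferred: that SAP 4.8 covers the other outcomes, and that standard of care may mean fewer than three counts a week (it could mean more). The first is supported by the SAP's own section numbering and by the unrestricted second sentence of the rule. The second is needed only for the weekly figures.

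The SAP also gives readers something to check against: missing counts by arm, a plot of median platelet count over time, and discontinuations for platelet recovery. These would help to expose an artefact but do not remove it.

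Finally, a reader might extend the point to the stopping criterion that begins "The participant has had 3 consecutive days with morning platelet counts", which cannot be observed day by day at home, and so to the per-protocol and instrumental variable results. Nothing in the documents allows an effect on those to be derived.

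**Conclusion.** The point holds in a limited form. Taken together, Protocol 8.4, SAP 4.5 and SAP 4.8 give the wrong level for the proportion of thrombocytopenic days in both arms: about 59% to 70% against a true 50% in the worked example. This follows from stated rules and is not just missing detail. A false between-arm difference is conditional on discharge timing differing by arm. For a gap of 2 to 3 days at three counts a week, the worked odds ratio runs from about 0.91 (discharge before recovery), through 1.01 (discharge either side of it), to 1.24 (discharge after it). All sizes rest on assumed lengths of stay and durations of low counts. The primary analysis and the sample size are not affected. It is worth correcting because the correction is cheap, not because a main result is at risk.

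**What to change.** Amend SAP 4.5, for all three thresholds, before database lock:

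- Put every day alive and under follow-up to study day 30 in the denominator. State one start day: SAP 4.5 now says consent, the SAP 5.7 table says randomisation, and SAP 2.2.3 says first administration.
- Classify a day without a count by linear interpolation between the adjacent recorded counts, and use the last count after the final measurement. The nearest recorded count is an acceptable alternative if a rule for ties is given.
- Treat days more than 6 days from any count as missing.
- State this as an exception to the no-imputation sentence in SAP 4.8.
- Keep the analysis of recorded days only as a sensitivity analysis.
- Report days in hospital by arm beside the result. These are already needed for the transfusion offsets in SAP 4.4.

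Do not use simple carry-forward, which extends the last low count past recovery, or the in-hospital denominator used for fever.

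The cost is a few SAP sentences and a table row or two. No new visit, blood test or data item is needed. The downside is some misclassification around recovery: about a day at three counts a week, more if counts are weekly.

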## Statistical Analysis Plan

---

### 4.6 Sub-Group analyses

Subgroup analyses will be performed for the primary outcome in the main analysis by including an interaction term. Analysis will be performed using the same methods as for the primary outcome, except a covariate and treatment-covariate interaction will be included in the model for each of the following variables in turn:

- Country of participant (UK vs. Australia), if evidence of heterogeneity between UK and Australian participants is identified in the interim analysis
- Platelet count at consent ( $\leq 30 \times 10^9/L$  vs.  $> 30 \times 10^9/L$ )

Treatment compliance during first 30 days of the trial (participant decided to stop taking trial treatment vs. participant did not decide to stop taking trial treatment). Although participants may decide to stop taking trial treatment for many reasons, the main reason is thought to be an unwillingness to take the large, over-encapsulated oral trial treatment. The over-encapsulated oral trial treatment is to be replaced with smaller tablets in the UK and Australia. Therefore, an additional analysis of treatment compliance will be performed using four mutually-exclusive categories: participant decided to stop taking trial treatment during the period of over-encapsulated oral treatment; participant decided to stop taking trial treatment during the period of oral treatment as tablets; participant did not decide to stop taking trial treatment during the period of over-encapsulated oral treatment; participant did not decide to stop taking trial treatment during the period of oral treatment as tablets. The number of UK participants who discontinued IV trial treatment during the period in September 2018 when oral treatment was unavailable will be described by arm.

### 4.7 Sensitivity analyses

- The key demographics and clinical condition of participants at consent will be described for each arm of the trial, comparing all randomised participants with the mITT population to ensure that excluded participants are similar across the arms.
- Per-protocol analysis of the primary outcome. This analysis will exclude all participants who did not adhere to a set of minimum protocol-adherence criteria during the first 30 days of the trial. Participants who were randomised in error will be excluded from this analysis. The per-protocol analysis will be performed using the same method as for the mITT analysis. Protocol-adherence will be summarised by treatment arm. In addition, since the per-protocol analysis may lead to an over-estimation of the difference in the proportion experiencing the primary outcome in each treatment arm, which may be explained by differing levels of protocol-adherence in each treatment arm, an instrumental variable analysis will be performed. The randomisation arm will be used as the instrument. The instrumental variable estimate will be calculated as the mITT estimate of the difference in the proportion experiencing the primary outcome in each treatment arm / proportion adhering to the minimum compliance criteria in the active treatment arm. The standard error of the instrumental variable estimate will be calculated using two-stage least squares.
- Some participants may withdraw or be lost to follow up during the conduct of the trial. In addition, some participants who are followed up for the full 30 days may be missing some bleeding assessments. In these cases, it is impossible to know whether such participants would be either less or more likely to experience bleeding if they had complete bleeding assessments for the full 30-day follow up period. Sensitivity of the primary outcome to incomplete follow up and missing bleeding assessments will be assessed by re-calculating the primary outcome, by arm, for all participants included in the mITT analysis, after imputing all missing bleeding assessments up to study day 30.

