#### 1.5.2 Primary efficacy outcomes

616 participants will be accrued to the UK/Australian clinical trial.

The participants will be randomised in a double blind fashion to receive TXA or a matching placebo.

The clinical trial will be conducted with the primary endpoint of decreased proportion of death or WHO Grade 2 or higher bleeding among all participants receiving TXA versus placebo over 30 days. The type 1 error will be controlled at a two-sided level of 0.05. The primary endpoint will be analysed using the Kaplan-Meier (KM) method to estimate the probability of bleeding or death within 30 days in the analysis populations. Power and sample size calculations are based on a log-rank test for comparing two survival curves, as described in Collett.

It is anticipated that the UK and Australia will be able to recruit 616 participants for this trial. Under the assumption that anti-fibrinolysis results in a decrease of death or WHO Grade 2 bleeding from 43% to 32%, the 616 participants will provide 80% power to detect an observed absolute decrease in bleeding rates of 11% (a relative reduction of 26% with a NNT of 8.9) and will be judged statistically significant at the two-sided 0.05 level. The planned trial size of 616 subjects includes an additional 5% of participants above the required sample size of 586. This 5% figure is more than the proportion of participants within TOPPS (4%) that dropped their platelet count below  $50 \times 10^9/L$  but did not drop their platelet below  $30 \times 10^9/L$ . This therefore accounts for the number of participants within the trial who are randomised but never receive the trial treatment.

We do not expect there to be a problem with the assessment of the primary outcome of bleeding over the 30 day trial period, starting from the first day of administration of the study intervention. In the recent TOPPS trial, completeness of bleeding outcome documentation was

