### 4.2.1 Efficacy population

The population used for efficacy analyses will be a modified intention to treat population (mITT) including all randomised participants whose platelet count falls to  $30 \times 10^9/L$  or below. Data are gathered for 30 days from the day the first dose of trial treatment is administered or is planned to be administered for those participants who did not receive treatment. Participants will be analysed in the arm that they were randomised to. Randomised participants whose platelet counts do not fall to  $30 \times 10^9/L$  or below will be excluded from the analysis, as will participants who develop exclusion criteria after randomisation and prior to their count falling to  $30 \times 10^9/L$  or below. These exclusions are deemed appropriate as the early randomisation is for pragmatic reasons only. Characteristics of all randomised participants will be compared to the mITT population to ensure that excluded participants are similar across the arms.

Unless otherwise specified, all analyses will be by this mITT. All subjects who fulfil the mITT requirements will be included in the analyses. Subjects whose platelet count falls to  $30 \times 10^9/L$  or below will be included in the analyses, even if they were randomised in error, did not receive trial treatment, stopped trial treatment "early", or received prophylactic transfusions not in accordance with the protocol.

**Rationale:** Owing to the emergent nature of treatment of thrombocytopenic participants, participants are randomised in a double blind fashion to the treatment arms when platelet levels drop below  $50 \times 10^9/L$ . This will allow time for the pharmacy to prepare the trial treatment, and for the trial treatment to be available when the platelet count falls to  $30 \times 10^9/L$  or below. This has been instituted for pragmatic reasons and will guard against delays in the availability of the trial treatment.

The main outcome analysis will be based on the mITT population. However, a per-protocol analysis of the primary outcome will also be performed. This per-protocol analysis will exclude all participants who were randomised in error and all participants who did not adhere to a set of minimum protocol-adherence criteria during the first 30 days of the trial. The criteria are:

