## Statistical Analysis Plan

### 5.9 Sensitivity and missing data analysis tables

**Table xx Baseline characteristics for all randomised participants vs. all randomised participants with platelet count  $\leq 30 \times 10^9/L$  – data are number (%) for categorical variables, and mean (SD) for continuous variables**

	Randomised participants		Randomised participants with platelet count $\leq 30 \times 10^9/L$	
	Active arm (n=)	Placebo arm (n=)	Active arm (n=)	Placebo arm (n=)
Male				
Age (years)				
Ethnicity				
White				
Asian				
Black African				
Black Caribbean				
Arab/other Middle East				
ancestry				
Aboriginal				
Other				
Mixed ethnic group:				
White/Black Caribbean				
White/Black African				
White/Asian				
White/Aboriginal				
White/Other				
Other mixed ethnic group				
Height (cm)				
Weight (kg)				
Diagnosis				
AML				
ALL				
APL				
CML				
CLL				
Hodgkins Lymphoma				
Non-Hodgkins Lymphoma				
Myeloma				
MDS				
Other				
Treatment plan				
Induction chemotherapy				
Consolidation chemotherapy				
Autograft				
Allograft				
Other				
Platelet count at consent ( $\times 10^9/L$ )				

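### The check on post-randomisation exclusions compares two overlapping sets, so it does not display, and is insensitive to, an imbalance among those excluded

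*SAP*

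**What the plan says.** SAP 4.2.1 builds the mITT from randomised participants whose platelet count reaches 30 × 10⁹/L or below. It drops people by two routes. The first is never reaching that count. The second is meeting an exclusion criterion in the interval before reaching it: "as will participants who develop exclusion criteria after randomisation and prior to their count falling to" that level. The stated justification is that randomisation is early for practical reasons only.

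The same section then promises a check: "Characteristics of all randomised participants will be compared to the mITT population to ensure that excluded participants are similar across the arms". SAP 4.7 repeats it as a description by arm, "comparing all randomised participants with the mITT population to ensure that excluded participants are similar across the arms".

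The template for this check in SAP 5.9 is titled "Baseline characteristics for all randomised participants vs. all randomised participants with platelet count" at or below 30 × 10⁹/L. It has two blocks, each split by arm with an n= heading, and the cell contents are specified as "data are number (%) for categorical variables, and mean (SD) for continuous variables". There is no block for excluded participants, no reason for exclusion and no p-value.

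The only planning figure that bears on how many will be excluded is in SAP 1.5.2: the total of 616 "includes an additional 5% of participants above the required sample size of 586". That allowance is described as covering participants who are randomised but never treated. It is supported by 4% in the earlier platelet trial whose count fell below 50 but not below 30. No rate is given for the second route.

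**The concern.** The stated aim concerns the excluded participants: are they alike in the two arms? The planned comparison is between everyone and nearly everyone. Two sets that share most of their members will look alike almost regardless of who was left out, so similar columns say little about the excluded group.

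There is a second, separate difficulty. The second block in 5.9 is headed by platelet count only. A participant excluded from the mITT for developing an exclusion criterion, whose count later falls to 30 or below, satisfies that heading and would sit among those apparently kept.

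At stake is how much a reader can conclude from this table about the departure from full intention to treat. The primary estimate itself is not in question here.

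**Working it through.** **Inputs.** Total 616, required 586 and the 5% allowance (SAP 1.5.2); 1:1 allocation (SAP 1.4), hence 308 per arm; event proportions 43% and 32%, two-sided 0.05, 80% power, log-rank method (SAP 1.5.2). The excluded share, the trait and its split are assumptions made for illustration.

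**The plan's own figures.** Hazard ratio = ln(0.68)/ln(0.57) = 0.686. Events = (1.960 + 0.842)² / (0.25 × (ln 0.686)²) = 221.2, rounded up to 222. Dividing by the mean event proportion 0.375 gives 592 (590 without rounding events), close to the stated 586. Allowance: 586 × 1.05 = 615.3, so 616. These figures hold together.

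**Share kept, if the allowance is the excluded share.** 586/616 = 95.1%. That is 30 excluded in total, or 15 excluded and 293 kept in each arm of 308.

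**Dilution.** In one arm, with n randomised, k kept and e excluded:

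p(all) = (k × p(kept) + e × p(excluded)) / n

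If those kept have the same proportion in both arms, the between-arm gap in the all-randomised block is (e/n) × (gap among the excluded). With e = 15 and n = 308 the factor is 0.0487, about 1/20. With e = 31 it is 31/308 = 0.101, about 1/10.

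**Example at 5%.** Take a trait present in 146/293 of those kept in each arm, and in 12/15 v 3/15 of the excluded (80% v 20%, Fisher p = 0.003).
- All randomised: (146 + 12)/308 = 51.3% v (146 + 3)/308 = 48.4%.
- Kept: 146/293 = 49.8% in both arms.
- The 60-point gap becomes 60 × 15/308 = 2.9 points. Within an arm, all randomised and kept differ by about 1.5 points.

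**Range.** The chi-square p-values are for scale only; the template has none.

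| Excluded per arm | Trait among excluded | Kept, each arm | All randomised | Chi-square p, all randomised |
|---|---|---|---|---|
| 12 (4%) | 10 v 2 | 50.0% | 51.3% v 48.7% | 0.52 |
| 15 (5%) | 12 v 3 | 49.8% | 51.3% v 48.4% | 0.47 |
| 15 (5%) | 15 v 0 | 49.8% | 52.3% v 47.4% | 0.23 |
| 31 (10%) | 25 v 6 | 49.8% | 52.9% v 46.8% | 0.13 |

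**Can the excluded group be recovered by subtraction?**
- Categorical rows, if the second block really is the mITT: yes. 158 − 146 = 12 and 149 − 146 = 3.
- Numbers excluded, on the same condition: yes, from the n= headings. For example, 25 v 5 excluded would show as 283 v 303 kept (Fisher p = 0.0002).
- Continuous rows: poorly. The excluded mean is (308 × M − 293 × m)/15, where M is the all-randomised mean and m the kept mean. With means printed to one decimal, the rounding error can reach (308 × 0.05 + 293 × 0.05)/15 = ±2.0 units.
- With the block as headed in 5.9: not in general. If x of the 15 were excluded for a new exclusion criterion and later fell to 30 or below, the block holds 293 + x and subtraction returns 15 − x. The x participants excluded by that route and later reaching 30 or below disappear from view.

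**The case against.** The strongest reply is that the table is by arm and gives counts, so a careful reader can subtract. That stands for categorical rows and for the numbers excluded, provided the second block is the mITT. A reader might therefore go too far in inferring that the table can never reveal an imbalance. It is insensitive and does not display the group, which is a weaker statement.

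A reader might also infer that this table is the only safeguard. The documents do not support that. A CONSORT diagram is planned (SAP 4.2 and 5.10), along with by-arm listings of withdrawals, randomisation errors and protocol deviations (SAP 5.2.2 to 5.2.5). The start of SAP 5.2 was not in the text I had, so I cannot say that numbers or reasons for exclusion are absent there. None of the listings I could see compares the baseline characteristics of the excluded.

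A third tempting inference is that the mITT comparison is biased, or that it rests on the exclusions being balanced. It rests on early randomisation being a practical device. Both routes close before trial treatment should begin, and participants and site staff are blinded (Protocol 5.8; trial pharmacists know the group but not what it is). Exclusions should then differ between arms only by chance. In the example above the analysed arms are balanced, and the 5.9 table would show that.

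On the column heading, SAP 4.2.1 and 4.7 both name the mITT as the comparator, and SAP 4.3 uses the same platelet-count shorthand for the primary analysis. A programmer might well apply the 4.2.1 definition. The texts still disagree, and the heading is what the template shows.

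**Conclusion.** The concern holds as a mismatch between a check's stated purpose and what its table displays. At an assumed 5% excluded, a difference among the excluded is diluted about 20-fold; at 10%, about 10-fold. The 5% is inferred from the sample-size allowance and is not a stated mITT share. The exclusion-criterion route has no stated rate, so the true share could be higher. The 80% v 20% split is illustrative and not a forecast.

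The heading mismatch in 5.9 removes the main remedy, because subtraction returns the excluded group only if the second block is the mITT of 4.2.1.

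This is a minor point. Large bias from these exclusions is unlikely, the primary result would not change, and no power or sample-size figure is wrong on this account. What changes is how much the check can support.

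**What to change.** In SAP 5.9, add or substitute a table of excluded participants only, by arm, with:
- the number excluded;
- the reason (count never 30 × 10⁹/L or below; developed an exclusion criterion first);
- key baseline variables.

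Redefine the second block of the existing template as the mITT of SAP 4.2.1, and reword 4.2.1 and 4.7 to point to the new table.

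Deaths and grade 2 or higher bleeds among the excluded may be listed descriptively from randomisation. They should not be set against the primary outcome, because these participants may have no day 1 and so no comparable 30-day window.

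The cost is one extra descriptive table. The baseline forms are already mandatory at consent (SAP 3.1, Table 1). With about 15 per arm it could show only gross differences, and the SAP should say so.
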